#### 9.7.1.1.3 EXPLORATORY ENDPOINTS

The exploratory endpoints are defined as follows.

- The seizure free rate in the 26-week Maintenance Period for subjects with POS by types of partial seizure
- The percent change in seizure frequency of POS per 28 days in the Maintenance Period and Extension Phase relative to the Pretreatment Phase
- The pharmacokinetics of perampanel as monotherapy
- The effect of perampanel on subjects' quality of life with EQ-5D-5L measurements

### 9.7.1.2 Definitions of Analysis Sets

#### **Safety Analysis Set**

The Safety Analysis Set is the group of subjects who sign informed consent, receive at least 1 dose of study drug and have at least 1 postdose safety assessment.

#### **Intent-to-Treat (ITT) Analysis Set**

The ITT Analysis Set is the group of subjects who sign informed consent, receive at least 1 dose of study drug and have at least 1 postdose primary efficacy measurement.

#### **Modified Intent-to-Treat (mITT) Analysis Set**

The mITT Analysis Set is the subset of the ITT Analysis Set who enter the 4 mg Maintenance Period and have at least 1 postdose primary efficacy measurement in the 26-week Maintenance Period.

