##### 9.7.1.6.1 PRIMARY EFFICACY ANALYSIS

The number (percentage) of subjects with POS who achieved seizure-free during the 26-week Maintenance Period of 4 mg and the corresponding 95% confidence interval (CI) will be calculated on the mITT Analysis Set. The primary interest of this study will be to confirm that the 95% lower CI is above the pre-specified threshold (ie, 40%). If subjects experience no seizures during the 4 mg Maintenance Period, those will be regarded as seizure-free in this analysis. Otherwise, subjects will be regarded as non-seizure-free.

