### 9.7.2 Determination of Sample Size

In this study, perampanel will be determined to be efficacious if, in untreated subjects with POS (including secondary generalized seizures), the lower limit of the 95% confidence interval for the seizure-free rate in the 26-week Maintenance Period is above the pre-specified threshold (40%).

Based on the results from research papers of AEDs for mono-therapy ([Chadwick, et al., 1999](#), [Arroyo, et al., 2005](#), [Mikkelsen, et al., 1981](#), [Heller, et al., 1995](#), and [Kaneko, et al., 2015](#)), the expected seizure free rate for other AEDs would be assumed 50.0%. According to [Glauser, et al. \(2013\)](#), the relative difference >20% versus the adequate comparator's efficacy point estimate could be considered non-inferior margin if its 95% lower confidence limit was above this lower acceptable cutoff ([Glauser, et. al., 2013](#)).

Under the assumption that the expected seizure free rate of perampanel in the 26-week Maintenance Period would be 60%, sample size of 72 will provide greater than 90% power that the lower limit of the 95% confidence interval for the seizure free rate in the 26-week Maintenance Period is above 40%. Taking into consideration the drop-out rate in the Titration Period (approximately 10%), 80 subjects need to be as the ITT Analysis Set.

If the number of subjects who achieve seizure-free is above the following criteria, this study can declare to confirm the efficacy of perampanel.

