**Table 6 Seizure free rate and 95% Confidence Interval**

| Target Number of mITT | Minimum Number of Subjects Who Achieve 26-week Seizure-free to Exceed the Pre-specified Threshold | Seizure-free Rate (95% CI) (%) a |
|-----------------------|---|---|
| 71                    | 38  | 53.5 (41.3, 65.5)                           |
| 72                    | 38  | 52.8 (40.7, 64.7)                           |
| 73                    | 38  | 52.1 (40.0, 63.9)                           |
| 74                    | 39  | 52.7 (40.7, 64.4)                           |
| 75                    | 39  | 52.0 (40.2, 63.7)                           |
| 76                    | 40  | 52.6 (40.8, 64.2)                           |
| 77                    | 40  | 51.9 (40.3, 63.5)                           |
| 78                    | 41  | 52.6 (40.9, 64.0)                           |
| 79                    | 41  | 51.9 (40.4, 63.3)                           |
| 80                    | 42  | 52.5 (41.0, 63.8)                           |
| 81                    | 42  | 51.9 (40.5, 63.1)                           |

CI = confidence interval, mITT = modified intent-to-treat.

a: 95%CI is based on Clopper-Pearson method.

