8.2 Efficacy Data Handling

Definition of Seizure-Free status

The definition of seizure-free for perampanel 4 mg will be as follows;

The subjects who completed the 4 mg Treatment Phase with no seizures will be treated as Seizure-Free status. The subjects who had any seizures will also be treated as Seizure-Free status only if the seizure(s) appeared after the Day 183 (ie, the target visit date of the 26th week of 4 mg Maintenance Period). Day 1 is the date of first dose of study drug in the 4 mg Maintenance Period. Otherwise, subjects will be regarded as non-Seizure-Free for the evaluation of perampanel 4 mg.

The definition of seizure-free for perampanel total (regardless of doses) will be as follows;

The subjects who completed the Treatment Phase of the last evaluated dose (ie, 4 or 8 mg) with no seizures will be treated as Seizure-Free status. The subjects who had any seizures will also be treated as Seizure-Free status if the seizure(s) appeared after the Day 183 (ie, the target visit date of the 26th week of Maintenance Period for the last evaluated dose). Day 1 here is the date of first dose of study drug in the Maintenance Period of the last evaluated dose. If subjects who were titrated up to 8 mg but down-titrated to 6 mg due to tolerability issue continued the study and completed the Maintenance Period with no seizure, those will also be treated as Seizure-Free status. Otherwise, subjects will be regarded as non-seizure-free.

Handling of seizure frequency

- **Baseline**

Baseline seizure frequency will be composed of the record based on the interview at visit 1 and the dispensed diary. Baseline seizure frequency will be calculated as the number of seizures per 12 weeks (see below).

$\frac{\text{Sum of seizures during baseline}}{\text{the number of days (84 days plus the study days during the Pretreatment Phase)}} \times 84$

Study days during the Pretreatment Phase will be the period between the date of obtaining informed consent and the date of first study drug dosing (ie, the date of study drug dispensing for visit 2).

- **Post-Baseline (Maintenance Period and Extension Phase)**

Post-baseline seizure frequency will be composed of the dispensed diary. Post-baseline seizure frequency will be calculated as the number of seizures per 12 weeks (see below). The Follow-up Phase will not be included in this analysis.

$\frac{\text{Sum of seizures during post-baseline}}{\text{the number of study days during post-baseline}} \times 84$

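### The primary analysis set drops 4 mg Maintenance entrants who leave no Maintenance seizure record, whereas the SAP counts all other non-completers as failures; only a borderline result would change

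*Protocol*

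**What the plan says.** Protocol section 9.7.1.2, the synopsis and SAP section 5.2.1 give the mITT set the same two conditions. A subject of the ITT set must enter the 4 mg Maintenance Period and must "have at least 1 postdose primary efficacy measurement in the 26-week Maintenance Period". Protocol section 9.7.1.6.1 makes this set the denominator of the primary rate: the "corresponding 95% confidence interval (CI) will be calculated on the mITT Analysis Set". Success requires the lower limit to exceed 40%, and a footnote to Protocol Table 6 states that "95%CI is based on Clopper-Pearson method".

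SAP section 8.2 defines the outcome. A subject is seizure-free on 4 mg after completing the 4 mg Treatment Phase without seizures, or if seizures came only after Day 183 of Maintenance. For everyone else: "Otherwise, subjects will be regarded as non-Seizure-Free for the evaluation of perampanel 4 mg".

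The sample size rests on an mITT of 72 and a true rate of 60%: "sample size of 72 will provide greater than 90% power". The only loss allowed for is the "drop-out rate in the Titration Period (approximately 10%), 80 subjects need to be as the ITT Analysis Set". SAP section 5.4.1 adds a sensitivity analysis of the primary endpoint on the ITT set.

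**The concern.** Two people who stop early in 4 mg Maintenance are handled in opposite ways, depending only on whether a Maintenance record reached the site. With a record, the subject is in the denominator as a failure. Without one, the subject leaves the denominator. A subject with no Maintenance record has not been shown to complete 26 weeks seizure-free, so under SAP section 8.2 that subject would be a failure if kept. The exclusion therefore works in one direction only, towards a higher rate. The trial has a single arm and a fixed 40% threshold, so no control group carries the same exclusion to offset it. At stake is the primary efficacy claim when the count is at or just above its minimum.

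**Working it through.** **Inputs.** Threshold 40%, assumed rate 60%, mITT of 72 and 10% Titration dropout (Protocol section 9.7.2); two-sided 95% Clopper-Pearson interval (Protocol Table 6). The number k of entrants without any Maintenance record is not in the documents; it is an assumption and a range is shown.

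**1. The plan's own figures.** The lower limit for x successes in n is the 2.5% quantile of a Beta(x, n − x + 1) distribution. For n = 72 it is 39.31% at x = 37 and 40.65% at x = 38, so the minimum is 38, as in Table 6. Power is P(X ≥ 38) for X ~ Bin(72, 0.60) = 91.4%, which agrees with the stated figure of over 90%. The one-sided error is P(X ≥ 38) for X ~ Bin(72, 0.40) = 1.9%. All 11 rows of Table 6 reproduce, and 72/0.90 = 80. The sample-size arithmetic is correct.

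**2. Restoring k excluded entrants as failures to an observed result.**

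| Observed on mITT | k | Restored | Lower limit | Above 40%? |
|---|---|---|---|---|
| 38/72 | 0 | 38/72 | 40.65% | yes |
| 38/72 | 1 | 38/73 | 40.04% | yes |
| 38/72 | 2 | 38/74 | 39.44% | no |
| 38/73 | 1 | 38/74 | 39.44% | no |
| 39/75 | 1 | 39/76 | 39.57% | no |
| 43/72 | 8 | 43/80 | 42.24% | yes |

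**3. False-claim rate when the k failures are dropped.** Take N entrants with a true rate of 40% among all of them, k being certain failures. The N − k who remain then have rate 0.40 × N/(N − k), and r is the minimum count for N − k. The error is P(X ≥ r) for X ~ Bin(N − k, 0.40 × N/(N − k)). For example, with N = 74 and k = 1: n = 73, rate 0.4055, r = 38 instead of 39, error 3.1%.

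| Entrants N | k=0 | k=1 | k=2 | k=4 |
|---|---|---|---|---|
| 72 | 1.9% | 1.9% | 3.2% | 5.1% |
| 73 | 2.5% | 2.4% | 2.3% | 3.8% |
| 74 | 1.8% | 3.1% | 3.0% | 4.8% |

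The benchmark is the nominal 2.5% per tail. The error rises only where the exclusions lower the required count. At 72 entrants with k=1, and at 73 with k=1 or 2, the count stays at 38 and there is no inflation.

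**4. Power if the k are kept as failures.** With 72 entrants and a 60% rate among those measured, power is P(X ≥ 38) for X ~ Bin(72 − k, 0.60): 91.4% (k=0), 89.1% (k=1), 86.4% (k=2), 79.4% (k=4).

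**5. The ITT sensitivity analysis.** With 80 in ITT, 42 successes are needed (41/80 has lower limit 39.81%; 42/80 has 41.02%). If 8 withdraw in Titration and count as failures, and the other 72 have a 60% rate, P(X ≥ 42) for X ~ Bin(72, 0.60) = 66.1%.

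**The case against.** **Reach.** Table 3 schedules the first Maintenance diary return after Visit 4 (Week 6) at Week 10, so a reader might infer that anyone who leaves between those visits vanishes. The documents do not support that. Protocol section 9.5.1.3 and Table 3 also require the diary back at the Early Discontinuation and Follow-up visits. Section 9.5.5 asks every discontinuing subject to complete the early discontinuation procedures and provides for contact by mail or phone with those who stop attending. A subject who withdraws in Week 7 and attends either visit returns a Maintenance diary, stays in mITT and counts as a failure. Nor are early seizures lost: a recorded Maintenance seizure is a measurement, and subjects moving to 8 mg return the diary at Visit 2a (Table 4). Only entrants who never return any Maintenance diary are excluded. This objection stands, and it is why k is probably small.

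**Weight.** A reader might also infer that the primary decision generally hangs on one or two subjects. That is true only at or near the minimum count. At a 60% rate with n = 72, the chance of exactly 38 successes is 4.3%, and 43/72 is safe with k as high as 8. This also stands.

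**The ITT analysis as a safeguard.** Entrants were due to return postdose diaries at Visits 3 and 4, so on a natural reading they belong to ITT. If all ITT subjects without a completed seizure-free 4 mg phase count as failures, ITT is stricter than the proposed set, and a pass on ITT implies a pass on the corrected mITT. The converse fails. ITT adds all Titration withdrawals at the same time, so under the assumptions of step 5 it would miss the threshold about a third of the time (100% − 66.1% = 33.9%) even with the drug performing as planned, and such a miss would say nothing about this exclusion. The SAP also does not say how ITT subjects who never reached Maintenance are classified.

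**Visibility.** SAP sections 5.2.1 and 5.2.2 report the size of each set, subject listings and disposition, so k could be worked out afterwards. That helps a reader of the report but leaves the prespecified primary denominator unchanged.

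**Conclusion.** The point holds within limits. The mITT definition is inconsistent with the SAP's own rule for non-completers, and the inconsistency can only favour success. For small k the one-sided error ranges from no inflation (72 entrants with k=1; 73 with k=1 or 2) to about 3% (74 entrants with k=1 or 2; 72 with k=2), and reaches 5.1% at 72 entrants with k=4. Only a result at or near the minimum count can be reversed, by one to two subjects in the cases shown. These figures assume that the excluded entrants would be failures and that the true rate is 40% among all entrants; k is assumed throughout. Nothing here supports a claim that the trial's error rate is inflated in general, or that a result near the planned 60% is in doubt. The change is still worth making, because it concerns the primary denominator and costs little.

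**What to change.** In Protocol section 9.7.1.2, the synopsis and SAP section 5.2.1, define mITT as all ITT subjects who take at least one dose in the 4 mg Maintenance Period, and remove the requirement for a Maintenance measurement. State that a subject with no Maintenance seizure record is non-seizure-free, as SAP section 8.2 already provides for other non-completers. Because mITT remains a subset of ITT, also state what counts as a primary efficacy measurement, which is not defined at present, so that a postdose Titration diary clearly places an entrant in ITT.

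This still leaves Titration withdrawals out of the primary set, as the sample size assumes. The cost is one sentence in three places, a primary rate that may be slightly less favourable, and the loss of power shown in step 4: from 91.4% to 89.1% at k=1 or 86.4% at k=2 with 72 entrants.

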### 9.7.1.3 Subject Disposition

The number (percentage) of subjects screened for study entry and screen failures, and the primary reason for screen failures will be summarized. The number (percentage) of treated subjects will be summarized as well as subjects who discontinued from the study treatment and reasons for discontinuation from study treatment.

### 9.7.1.4 Demographic and Other Baseline Characteristics

Demographic and other baseline characteristics for the Safety Analysis Set will be summarized using descriptive statistics. Continuous demographic and baseline variables include age, height, weight, and body mass index (BMI); categorical variables include sex, age group (<65 years, ≥65 years). This summary table will be generated on the ITT Analysis Set if the Safety Analysis Set and the ITT Analysis Set are not identical. This summary table will also be generated on the mITT Analysis Set.

### 9.7.1.5 Prior and Concomitant Therapy

All investigator terms for medications recorded in the CRF will be coded to an 11-digit code using the World Health Organization Drug Dictionary (WHO DD). The number (percentage) of subjects who took prior and concomitant medications will be summarized on the Safety Analysis Set by Anatomical Therapeutic Chemical (ATC) class (ie, anatomical class, therapeutic class, pharmacologic class, chemical class), and WHO DD preferred term.

This summary table will be generated on the ITT Analysis Set if the Safety Analysis Set and the ITT Analysis Set are not identical.

Prior medications will be defined as medications that stopped before the first dose of study drug. Concomitant medications will be defined as medications that (1) started before the first dose of study drug and were continuing at the time of the first dose of study drug, or (2)

started on or after the date of the first dose of study drug up to the completion or discontinuation of the subject after the subject's last dose. All medications will be presented in subject data listings.

#### 9.7.1.6 Efficacy Analyses

All efficacy analyses will be performed based on the mITT Analysis Set unless otherwise noted.

##### 9.7.1.6.1 PRIMARY EFFICACY ANALYSIS

The number (percentage) of subjects with POS who achieved seizure-free during the 26-week Maintenance Period of 4 mg and the corresponding 95% confidence interval (CI) will be calculated on the mITT Analysis Set. The primary interest of this study will be to confirm that the 95% lower CI is above the pre-specified threshold (ie, 40%). If subjects experience no seizures during the 4 mg Maintenance Period, those will be regarded as seizure-free in this analysis. Otherwise, subjects will be regarded as non-seizure-free.

##### 9.7.1.6.2 SECONDARY EFFICACY ANALYSES

The number (percentage) of subjects with POS who achieved seizure-free during the 26-week Maintenance Period regardless of perampanel dose and the corresponding 95% CI will be calculated on the mITT Analysis Set. To examine if the 95% lower CI exceeds the threshold (ie, 40%) is the key secondary efficacy analysis.

The number (percentage) of subjects in the mITT population with POS who achieved seizure-free during the 52-week treatment (ie, 26-week Maintenance Period and 26-week Extension Phase) and the corresponding 95% confidence interval (CI) will be calculated.

Median time to first seizure onset will be estimated by Kaplan-Meier method. Time to first seizure onset will be defined as the time from the first date of Maintenance Period to the date of first seizure onset during the Maintenance Period. Subjects who withdraw from the study before first seizure onset will be censored at the time of study discontinuation.

Median time to withdraw from the study will be estimated by Kaplan-Meier method. Time to withdraw from the study will be defined as the time from the first date of Maintenance Period to the date of discontinuation from the study. Subjects who are ongoing at the data cutoff will be censored at the time of data cutoff.

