## 24. Subject who is diagnosed with dementia

### 9.3.3 Removal of Subjects From Therapy or Assessment

The investigator may withdraw the subject from the study at any time for safety or administrative reasons. The subject may stop study drug or withdraw from the study at any time for any reason.

A subject who discontinues study treatment should be followed for subsequent protocol-specified visits and procedures. The primary reason for discontinuation contributing to the subject's discontinuation from study drug(s) should be collected. If subjects need to take other AEDs because of insufficient efficacy of perampanel, they will discontinue the study. The first date when other AEDs are administered will be defined as the final date of perampanel monotherapy, and the subsequent date when the perampanel is completely withdrawn will be defined as the discontinuation date of the study.

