#### **9.5.1.3 Efficacy Assessments**

Efficacy will be assessed by seizure counts and types as recorded on the diary.

Diaries will be dispensed to all subjects and returned from all subjects at each visit as described in Table 3. The diary is to be completed by the subject or the caregiver. All seizure counts and types will be recorded. At each visit the subject or the caregiver will be instructed by the site personnel as to how to complete the diary and reminded that they must return the diary at their next scheduled clinic visit and at the Early Discontinuation and Follow-up Visits (if applicable). To ensure correct seizure classification, the medically qualified investigator should review the diary with the subject or the caregiver at all visits. Subjects or caregivers must be counseled if diary compliance is not satisfactory.

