### 9.5.5 Completion/Discontinuation of Subjects

A subject may elect to discontinue the study at any time for any reason. All subjects who discontinue the study are to complete the study's early discontinuation procedures indicated in the Schedule of Procedures/Assessments (Table 3 and Table 4).

The investigator will promptly explain to the subject involved that the study will be discontinued for that subject and provide appropriate medical treatment and other necessary measures for the subject. A subject who has ceased to return for visits will be followed up by mail, phone, or other means to gather information such as the reason for failure to return, the status of treatment compliance, the presence or absence of AEs, and clinical courses of signs and symptoms.

Subjects who discontinue early from the study will be discontinued for 1 of these primary reasons. Study disposition information will be collected on the Subject Disposition CRF.

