5.4.2 Secondary Efficacy Analyses

The number (percentage) of subjects with POS who achieved seizure-free during the 26-week Maintenance Period regardless of perampanel dose and the exact corresponding 95% CI will be calculated. To examine if the 95% lower CI exceeds the threshold (ie, 40%) is the key secondary efficacy analysis. The 26-week Maintenance Period mentioned here is the Maintenance Period of the last evaluated dose (ie, 4 or 8mg).

The number (percentage) of subjects with POS who achieved seizure-free during the 52-week treatment of 4 mg (ie, 26-week Maintenance Period of 4 mg and 26-week Extension Phase) and the corresponding 95% CI will be calculated.

The number (percentage) of subjects with POS who achieved seizure-free during the 52-week treatment (ie, 26-week Maintenance Period and 26-week Extension Phase) and the corresponding 95% CI will be calculated. The 26-week Maintenance Period mentioned here is the Maintenance Period of the last evaluated dose.

Median, Q1 and Q3 time to first seizure onset will be estimated by Kaplan-Meier method. The cumulative probability of the event (ie, seizure occurrence) at every 26 weeks will also be calculated. Corresponding 2-sided 95% CIs will also be presented. Kaplan-Meier estimates of the time to event will be plotted over time. The Follow-up Phase will not be included in this analysis. The above analysis will be summarized for the entire study period of 4 mg and the entire study period of the last evaluated dose, respectively.

Time to first seizure onset will be defined as the period from the first dose of study drug in the Maintenance Period of the last evaluated dose to the first seizure onset. The censoring rule for the analysis of time to first seizure onset will be provide in the [section 8](#).

Median, Q1 and Q3 time to withdraw from the study will be estimated by Kaplan-Meier method. The cumulative probability of the event (ie, withdraw from the study) at every 26 weeks will also be calculated. Corresponding 2-sided 95% CIs will also be presented. Kaplan-Meier estimates of the time to event will be plotted over time. The Follow-up Phase will not be the period to be analyzed. The above analysis will be summarized for the entire study period of 4 mg and the entire study period of the last evaluated dose, respectively.

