Study days during the post-baseline of maintenance period will be the period between the date of study drug dispensing for the Maintenance Period of the last evaluated dose and the disposition data in maintenance period of the last evaluated dose. Study days during the post-baseline of extension phase will be the period between the disposition data in maintenance period of the last evaluated dose and the date of data cutoff or the date of study discontinuation, whichever comes first.

the data on seizure expression that obtained during the Titration Period and the Follow-up Phase will be presented only in the subject data listing.

Handling of missing data

- **Seizure frequency**

If subjects have a missing seizure count in any of each seizure type (ie, simple partial with motor signs, simple partial without motor signs, complex partial, and complex partial with secondarily generalized seizure) for each unique diary record, the overall seizure frequency for that record will be handled as missing data. Similarly, if complex partial and/or complex partial with secondarily generalized seizure are missing for each unique diary record, then complex partial seizure plus secondary generalized seizure frequency will be handled as a missing data.

- **EQ-5D-5L**

No imputation will be performed for the missing value.

Censoring rules for time to event analysis

1. The censored rule for the analysis of time to first seizure onset will be provided in the following table. If subjects met multiple censoring criteria, the censoring date will be the earliest date of them.

No.	Situation	Date of Event or Censoring	Outcome
1	Seizure onset	Date of the first seizure onset	Event
2	Withdraw from the study	Date of study withdrawal	Censored
3	Ongoing at the data cutoff (with no seizure)	Date of data cutoff (each subject's final non-missing assessment date)	Censored

2. The censored rule for the analysis of time to study withdrawal will be provided in the following table. If subjects met multiple censoring criteria, the censoring date will be the earliest date of them.

No.	Situation	Date of Event or Censoring	Outcome
1	Withdraw from the study	Date of study withdrawal	Event
2	Ongoing at the data cutoff	Date of data cutoff (each subject's final non-missing assessment date)	Censored

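### Time to first seizure: withdrawn subjects are censored at the withdrawal date and ongoing subjects at their last assessment, so unobserved days before a withdrawal can count as seizure-free time

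*Protocol*

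**What the plan says.** Time to first seizure onset is a secondary endpoint. For subjects who leave without a seizure, Protocol 9.7.1.6.2 (repeated in the synopsis) says: "Subjects who withdraw from the study before first seizure onset will be censored at the time of study discontinuation". In SAP 8.2, row 2 of the first censoring table carries this over as "Date of study withdrawal". Row 3, for subjects ongoing and seizure-free at cutoff, qualifies the cutoff date as each subject's "final non-missing assessment date". It does not say which assessment is meant. Where several censoring criteria apply, the earliest date is used.

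Protocol 9.5.1.3 gives the source of the events: "Efficacy will be assessed by seizure counts and types as recorded on the diary". The diary is to be returned at the next scheduled visit and, where they apply, at the Early Discontinuation and Follow-up Visits. Tables 3 to 5 mark its return and review at the Early Discontinuation Visit.

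For subjects who stop attending, Protocol 9.5.5 says: "A subject who has ceased to return for visits will be followed up by mail, phone, or other means". Neither document says how their discontinuation date is set. The missing-diary rule in SAP 8.2 concerns seizure frequency, not time to first seizure. SAP 5.4.2 adds of the time-to-first-seizure analysis: "The Follow-up Phase will not be included in this analysis". It also adds cumulative probabilities at every 26 weeks, with confidence intervals and a plot, to the median planned in the protocol.

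**The concern.** A Kaplan-Meier risk set should hold only subjects whose event would be seen if it happened. Row 3 of the SAP table moves towards that principle by stopping at the last assessment. Row 2 does not: it stops at the withdrawal date, whether or not the diary reaches that far. One curve therefore uses two definitions of the end of observation.

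The earliest-date clause does not reconcile them. A withdrawn subject meets the withdrawal criterion only. He or she is not ongoing at cutoff, so the row 3 date never enters the comparison.

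At stake is a modest favourable bias in a secondary curve of an open-label, single-arm trial, where no control group shares the error.

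**Working it through.** **The plan's own figure.** The documents give no numerical target for time to first seizure. Their stated figure belongs to the primary endpoint, and it reproduces. With 72 subjects and success at 38 or more seizure-free, exact binomial power is 91.4% at a true rate of 60%, and the one-sided error is 1.9% at 40%. Enrolment is 72/(1 − 0.10) = 80. None of this depends on the censoring rule, because SAP 8.2 classes subjects who leave the 4 mg phase early as non-seizure-free.

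**Direction.** The estimate is S(t) = Π(1 − d_j/n_j), with d_j events and n_j subjects at risk at each event time. Moving a censoring date from the last diary day to a later withdrawal date leaves every d_j unchanged, because unseen seizures are not counted, and leaves each n_j equal or larger. Every factor is then equal or larger, so S(t) cannot fall.

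**Inputs for the size.**
- Seizure-free at week 26: 60% (Protocol 9.7.2). With a constant hazard, λ = −ln(0.60)/26 = 0.0196 per week.
- Visit spacing in Maintenance: 4 to 6 weeks (Protocol Tables 3 and 4). In the Extension it is 6 to 8 weeks and later 12 (Table 5).
- Assumed, because the documents give neither: 5%, 10%, 20% or 30% withdrawal over 26 weeks, independent of seizures, and a diary gap of 2, 4, 6 or 12 weeks for every withdrawn subject. The only dropout figure in the plan is about 10%, for Titration.

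**Simulation.** There were 600 trials of 72 subjects per scenario. Each was analysed with censoring at withdrawal and with censoring at the last diary day. Mean excess of the week-26 seizure-free estimate under the plan's rule, in percentage points:

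| Withdrawal | 2-week gap | 4-week gap | 6-week gap | 12-week gap |
|---|---|---|---|---|
| 5% | 0.1 | 0.2 | 0.3 | 0.6 |
| 10% | 0.2 | 0.5 | 0.7 | 1.3 |
| 20% | 0.5 | 1.0 | 1.5 | 2.6 |
| 30% | 0.8 | 1.6 | 2.4 | 4.1 |

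In all 9,600 trials (16 × 600) the plan's rule gave the higher curve or a tie. With no gap the difference is zero.

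**Hand check.** With withdrawal rate μ and gap g, roughly a share μg of the risk set is unobserved, so S(26) ≈ 0.60^(1 − μg). At 10% withdrawal, μ = −ln(0.90)/26 = 0.00405. With g = 4, μg = 0.0162 and 0.60^0.9838 = 0.605, an excess of 0.5 points, as simulated. At 20% and 6 weeks, μ = 0.00858, μg = 0.0515 and the excess is 1.6 points, against 1.5 simulated. The approximation runs high for long gaps: in the simulation, subjects who would withdraw after week 26 have no gap.

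**The opposite case.** If the diary runs 4 weeks past withdrawal, as the follow-up diary can, the plan's rule censors earlier than the last diary day. At 10% withdrawal the curve under the plan's rule was then higher in 200 of 600 trials and lower in 398, with a mean difference of about 0.0 points. The one-way direction therefore belongs to gaps before withdrawal only.

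**The case against.** The strongest reply is that the schedule already closes the gap for most withdrawals. All subjects who discontinue are to complete the early discontinuation procedures (Protocol 9.5.5), which include diary return. For a subject who does so on the discontinuation date with a complete diary, the two censoring dates agree. This stands, and it limits the point to subjects who stop attending or whose diary ends early.

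A reader might infer more than the documents support in three ways.
- That every withdrawal inflates the curve, or that the rule can only push it up. The scheduled diary return and the opposite case above contradict this.
- That a subject who stops attending is recorded as discontinued at least one visit interval later, plus tracing time, with no seizure information gathered. No text dates discontinuation for these subjects; it could be the last visit, in which case there is no gap. The tracing list in 9.5.5 is illustrative and includes the clinical course of signs and symptoms, which may well cover seizures.
- That taper time counts as at risk while taper seizures are dropped. Where other antiepileptic drugs are needed, Protocol 9.3.3 says "the subsequent date when the perampanel is completely withdrawn will be defined as the discontinuation date of the study", so that date can fall late. But SAP 5.4.2 excludes the Follow-up Phase as a whole, and the natural reading removes its events and its time together.

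It is also fair to say that the effect is small. It can be set against a binomial standard error of √(0.60 × 0.40/72) = 5.8 points. Under the 60% assumption the median is not reached by week 26. SAP 8 leaves data handling to be settled before database lock, and SAP 9 places derivations in separate documents, so the gap may be closed there. That does not remove the point: the rule written in the SAP is the withdrawal date, and the same table treats ongoing subjects differently.

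**Conclusion.** The concern holds, at minor severity. Row 2 and row 3 of the same censoring table end observation differently. For subjects with unobserved days before the recorded withdrawal date, row 2 can count those days as seizure-free, and the resulting bias in the Kaplan-Meier seizure-free estimate is upward.

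At week 26 the excess is about 0.1 to 1.5 points for 5% to 20% withdrawal and gaps of 2 to 6 weeks, and about 2.6 points at 20% with a 12-week gap. These figures assume a constant hazard with 60% seizure-free at week 26, withdrawal independent of seizures, and a gap for every withdrawn subject. If only some withdrawn subjects have a gap, the effect is smaller. Readings after week 26 were not quantified here.

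The primary endpoint and its power are untouched. No success threshold attaches to this curve, and SAP 5.3.3 plans no statistical comparison.

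**What to change.** In SAP 8.2, first censoring table:
- Row 2: censor at the earlier of the date of study withdrawal and the last date with a non-missing seizure (diary) assessment, excluding the Follow-up Phase. The earlier-of form is needed because the last diary date alone could run past withdrawal.
- Row 3: state that the final non-missing assessment is also the last seizure (diary) assessment.

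Record the change in SAP section 7, and align Protocol 9.7.1.6.2 and the synopsis if the protocol is next amended. Leave the time-to-withdrawal table as it is.

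The cost is a short SAP edit and one derivation from diary data already collected, settled before database lock. Where diaries end early, follow-up time is slightly shorter and the estimate slightly less favourable and less precise. If every diary reaches the withdrawal date, the handling of withdrawals gives the same result as now.
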